Power: Sample sizes were calculated to provide sufficient power to calculate differences in our primary outcome (CR adherence, as measured by % completing 30+ sessions) between the control condition and any of the three intervention conditions as well as between the combined intervention and either of the interventions delivered alone. Of most relevance, preliminary data from a previous trial on the use of incentives to increase CR rates among lower-SES individuals show that 54% of those receiving incentives completed the 30+ sessions compared to 28% of those receiving usual care. Using these proportions and the likelihood ratio test for two proportions in SAS POWER, 57 individuals per condition would be needed to detect a significant difference between conditions with 80% power. A seminal set of studies, conducted by Co-I [name], that systematically determined the efficacy of case management and incentives, alone and in combination, on cocaine abstinence, provided additional data for the power estimates.⁵⁴⁻⁵⁸ Using effect sizes from these five studies, the maximum estimated number of participants needed per condition is 50 to detect a significant difference in treatment adherence in combined intervention vs. single intervention with 80% power. Comparing any of the interventions singly or combined to usual care at four months post-treatment is estimated to require at most 25 participants per condition. Supporting these estimates, additional studies on the use of case management or incentives for adherence to other health-related behaviors have demonstrated effect sizes comparable to the studies referenced above.^{66,67,73,106,107} As such, the proposed sample size of 209 randomized subjects (57/intervention condition, 38 control) will allow us to conduct all pre-planned pairwise comparisons of the primary outcome measure (program adherence) with 80% power.

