Note: Only those individuals authorized to solicit consent may sign the consent form confirming that the prospective subject was provided the necessary information and that any questions asked were answered.

Patients who are hospitalized, or being cared for, due to a recent cardiac event and are enrolled in Medicaid, or have less than a high school education will be approached for possible inclusion by the PI or a trained representative. Patients will be given an unlimited amount of time to decide about participating in the study. A consent form with appropriate HIPAA language will be used for this study. Patients will have the option of electronic consent or consenting in person. UVM Staff will email a unique link to a redcap survey. We will go through the consent form verbally over the phone and the patient will have an opportunity to ask any questions they may have prior to consenting to be in the study.

Information Withheld From Subjects: Will any information about the research purpose be withheld from potential or participating subjects? If so, explain and justify the non-disclosure and describe plans for post-study debriefing.

Not applicable

Statistical Analysis Plan

Sample Size and Power

Sample sizes were calculated to provide sufficient power to calculate differences in our primary outcome (CR adherence, as measured by % completing 36 sessions) between the control condition and any of the three intervention conditions as well as between the combined intervention and either of the interventions delivered alone. Estimates were based on a series of studies conducted within our research group.

Of most relevance, preliminary data from our prior trial on the use of incentives to increase CR rates among lower-SES individuals showed 54% of those receiving incentives completed the 36 sessions compared to 28% of those receiving usual care. Using these proportions and the likelihood ratio test for two proportions in SAS POWER, 56 individuals per condition would be needed to detect a significant difference between conditions with 80% power.

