A seminal set of studies, conducted by a member of our research team (Co-I [name]), that systematically determined the efficacy of case management and incentives, alone and in combination, provided additional data for the power estimates. This set of studies, conducted in the 1990's and early 2000's compared treatment conditions in programs for achieving cocaine abstinence among individuals with cocaine dependency.⁵⁴⁻⁵⁸ Although the primary outcome variable of these studies – cocaine abstinence, either continuously or at selected time points – differs from this study's focus on CR attendance, they are similar in terms of providing case management services, with or without incentives, to demographically comparable individuals to boost their EF, improving adherence to a program attempting to change behavior, and thereby instill long-term health benefits. Two of these earlier studies^{56,57} compared the effects of a community reinforcement approach (i.e., case management) with incentives to usual care in achieving continuous cocaine abstinence at the end of four to 16 weeks of treatment. The third study⁵⁴ tested the effects of the addition of incentives vs. usual care. Using condition proportions who achieved continuous cocaine abstinence at these time periods and the likelihood ratio test for two proportions in SAS POWER, we calculate sample size of each treatment condition vs. usual care required a maximum of 25 participants to achieve 80% power.

Subsequent studies examined initial cocaine abstinence among individuals with cocaine dependence comparing case management with and without incentives, case management with contingent incentives versus case management with non-contingent incentives, and case management with incentives versus incentives only.^{58,161,162} Across all of these permutations of combined intervention vs. single intervention, the maximum number of participants needed per condition to detect a significant difference between incentives or case management alone vs incentives and case management in combination in treatment adherence with 80% power was 50, again using the likelihood ratio test for two proportions in SAS POWER.

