In the literature, studies on the use of case management or incentives for adherence to other health-related behaviors have demonstrated effect sizes comparable to the studies referenced earlier,^{66,67,106,107} providing additional evidence that those prior studies are appropriate for estimating sample sizes for the proposed study. Thus, we estimate that 57 participants per treatment condition (i.e., case management only, incentives only, and case management with incentives) and 38 participants in the usual care condition will allow us to conduct all pre-planned pairwise comparisons of the primary outcome measure (program adherence) with 80% power.

Randomization

Stratified random allocation of participants will be used to assign individuals to conditions, using two dichotomous variables to stratify the sample: age (<57 years of age vs. ≥ 57) and smoking status (current smoker vs. former/non-smoker). Age and current smoking were the two demographic variables which significantly predicted CR attendance in the prior trial. As median age in our prior trial was 57, and 40% of participants were current smokers, stratifying using the proposed cut-offs will result in randomization cell sizes of appropriate size. Participants will be allocated to conditions using a 3:3:3:2 routine, whereby for every three individuals assigned to one of the three treatment conditions (case management only, incentives only, and case management plus incentives), two individuals will be assigned to the control condition (usual care). Assignment of participants to conditions will be conducted using the stratified block design method¹⁶³ in the

Interactive Voice Recognition (IVR) system maintained by the Medical Biostatistics Unit at the University of Vermont. Using this system will allow us to allocate participants over time, as they become eligible, while still maintaining desired arm counts across conditions.

Primary and Secondary Data Analyses

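### Incentives versus usual care has about 72% power, not 80%: the 57 per condition was derived for equal arms, but usual care gets 38

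*Combined protocol and SAP*

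**What the plan says.** **Planning rates.** The protocol (Statistical Considerations, Power) takes its most relevant figures from an earlier trial of incentives in the same setting: "54% of those receiving incentives completed the 30+ sessions compared to 28% of those receiving usual care". Using the likelihood ratio test for two proportions, it concludes that "57 individuals per condition would be needed to detect a significant difference between conditions with 80% power". The SAP (Sample Size and Power) uses the same rates and test and reports that "56 individuals per condition would be needed to detect a significant difference between conditions with 80% power".

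**Second sizing basis.** Both documents also draw on cocaine-abstinence studies. For any intervention against usual care, the protocol says the comparison "is estimated to require at most 25 participants per condition". The SAP says each such comparison "required a maximum of 25 participants to achieve 80% power". It attributes this to two studies of case management with incentives against usual care and a third that "tested the effects of the addition of incentives vs. usual care". The abstinence rates are not reported. For the combined intervention against either single one, at most 50 per condition are said to be needed.

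**Arm sizes and claim.** The SAP (Randomization) allocates 3:3:3:2, giving 57 in each intervention arm and 38 in usual care. The protocol then concludes that "the proposed sample size of 209 randomized subjects (57/intervention condition, 38 control) will allow us to conduct all pre-planned pairwise comparisons", with 80% power. The SAP gives the same arm sizes and the same conclusion. The planned comparisons include usual care against each of the three interventions, tested two-sided at 0.05.

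**The concern.** A sample size of 56 or 57 per condition, derived for two equal arms, does not carry over to a comparison in which one arm has 38. The variance of a difference in proportions depends on both arm sizes. As a rough guide, 57 versus 38 carries the information of an equal-arm comparison with 2 × 57 × 38 / 95 = 45.6 per arm, well below 56. Neither document shows a power calculation for 57 versus 38.

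Incentives versus usual care is the only primary comparison with cardiac rehabilitation rates behind it. If its power is overstated, a non-significant result would be read as coming from a test with a 20% chance of missing the planned effect, when the plan's own inputs imply a larger one.

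**Working it through.** **Inputs.** Rates 54% and 28%, and the likelihood ratio test for sizing: protocol, Power. Two-sided 0.05 and a z test for two proportions as the planned analysis: protocol, Data Analysis. Arm sizes 57 and 38: protocol, Power, and SAP, Sample Size and Power. No multiplicity adjustment is stated and none is applied here.

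**Formula.** With p̄ the average of the two rates weighted by arm size, the noncentrality is

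λ = 2 Σ nᵢ [pᵢ ln(pᵢ/p̄) + (1 − pᵢ) ln((1 − pᵢ)/(1 − p̄))]

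and power = Φ(√λ − 1.96) + Φ(−√λ − 1.96). The second term is negligible here.

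**Step 1: the plan's figure, equal arms.** p̄ = 0.41. The bracketed terms are 0.03423 (at 54%) and 0.03659 (at 28%), which sum to 0.07082.

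- 55 per arm: λ = 7.790, power 79.7%
- 56 per arm: λ = 7.932, power 80.4%
- 57 per arm: λ = 2 × 57 × 0.07082 = 8.073, √λ = 2.841, power 81.1%

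The minimum is 56, so the plan's 56 and 57 are equal-arm numbers.

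**Step 2: the actual arms, 57 versus 38.** p̄ = (57 × 0.54 + 38 × 0.28)/95 = 41.42/95 = 0.436. The bracketed terms become 0.02176 and 0.05182.

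λ = 2 × (57 × 0.02176 + 38 × 0.05182) = 6.419, √λ = 2.534, power = Φ(0.574) = **71.7%**.

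**Step 3: does the choice of test matter?** Power at 57 versus 38, 54% versus 28%, two-sided 0.05:

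| Test | Approximation | Exact enumeration |
|---|---|---|
| Likelihood ratio | 71.7% | 72.8% |
| z, pooled variance | 71.7% | 71.6% |
| z, unpooled variance | 75.3% | 74.8% |
| Arcsine | 72.5% | – |
| Fisher | – | 68.0% |

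None of these reaches 80%. A one-sided 0.05 test would (81.8%), but the plan specifies two-sided.

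**Step 4: what would give 80% (likelihood ratio test).**

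- Keeping 57 versus 38 and a 28% control rate: an intervention rate of about 57% (79.9% power at 56.8%, 80.4% at 57%). The detectable difference is about 29 points instead of 26.
- Keeping 57 on incentives and 54% versus 28%: about 55 controls (54 falls just under 80%, 55 gives 80.4%).

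**Step 5: the figure of 25 per condition.** At 54% versus 28%, 25 per arm gives λ = 2 × 25 × 0.07082 = 3.541 and power 46.9% (about 51% by exact enumeration of the pooled z test). So 25 and 57 cannot both answer the same question for incentives versus usual care; they assume different effects. If control is taken as 28%, 25 per arm reaches 80% only at an intervention rate of about 67%.

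**Step 6: the other two comparisons with usual care.** The documents give no cardiac rehabilitation rate for case management alone or for the combination. Assuming 28% in usual care, 57 versus 38 has this power (likelihood ratio test):

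| Assumed intervention rate | Power |
|---|---|
| 50% | 57.8% |
| 54% | 71.7% |
| 60% | 87.3% |
| 65% | 94.7% |
| 67% | about 97% |

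**The case against.** The best defence is that the plan sizes the comparisons with usual care separately, at no more than 25 per condition, and 38 exceeds 25. Under the effects behind that estimate the claim is true. An effect giving 80% at 25 per arm gives about 96% to 97% at 57 versus 38, for assumed control rates from 5% to 40%. On this reading the defect is reliance on the more optimistic of two planning effects rather than a slip in arithmetic. Two estimates from different populations and outcomes may also legitimately differ.

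Part of this stands. The documents do not show that 25 is wrong, and larger effects would give ample power. But the plan itself ranks 54% versus 28% as its most relevant evidence, and the SAP acknowledges that the cocaine studies measured a different outcome. Their rates are not given, so the estimate cannot be checked. The three studies the SAP lists behind the 25 include none of case management alone against usual care. Above all, the 80% claim is stated without condition, directly after rates at which it fails.

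Two smaller points are fair. The plan does not say whether the z test pools the variance, so a range of about 72% to 75% covers that choice. And the shortfall is modest beside the uncertainty in a pilot estimate whose size and precision are not reported. Neither brings the power to 80%.

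**Conclusion.** The claim of 80% power for every planned pairwise comparison is wrong as written. At 54% versus 28%, two-sided 0.05, with 57 on incentives and 38 on usual care, power is 71.7% by the plan's own sizing test, about 8 points below the stated figure; the type II error is about 28%. The conclusion rests only on the plan's rates, significance level and arm sizes.

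It is confined to incentives versus usual care at those rates. For case management alone and for the combination against usual care, power depends on rates the documents do not give. The comparisons of the combination with each single intervention (57 versus 57, at most 50 said to be needed) are not affected by the size of the control arm and are not disputed.

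**What to change.** Replace the blanket 80% statement in the protocol (Statistical Considerations, Power) and in the SAP (Sample Size and Power). Suggested content:

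- Comparisons with usual care (57 versus 38) have about 72% power for 54% versus 28%, or 80% power for about 57% versus 28%, by the likelihood ratio test at two-sided 0.05.
- Power of 80% or more against usual care for other effects depends on the larger effects taken from the cocaine-abstinence studies.
- The statement on the combination versus either single intervention stays as it is.

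The protocol attaches 54% and 28% to completing 30 or more sessions, and the SAP attaches them to completing 36. That is a separate inconsistency and does not change the arithmetic, but the revised sentence should name the endpoint to which the rates belong.

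The cost is wording in two places. No patients are added, and allocation and analysis stay the same. The stated power for incentives versus usual care becomes less favourable.

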If the CR clinics (UVMMC, Copley Hospital, Northwestern Medical Center) cease in-person visits, session completion will be calculated by tracking remote participation. Study participants across arms will be expected to complete two CR sessions per week. One session will consist of completing the weekly telemedicine call conducted by CR staff and one session will consist of completing a recommended step goal for that day, as confirmed by an Omron pedometer. A session will be coded as missed (excused or unexcused, depending on the situation) if a participant fails to send a step count or fails to complete the telemedicine call from the CR case manager.

For research involving survey, questionnaires, etc.: Describe the setting and the mode of administering the instrument and the provisions for maintaining privacy and confidentiality. Include the duration, intervals of administration, and overall length of participation. (describe and attach all instruments)

Not applicable

Questionnaires will be administered at intake, after 4 months, and at one year. All questionnaires will be administered in a private setting at the Cardiac Rehabilitation Facility. Questionnaires should take approximately one hour to complete.

As listed above the following questionnaires will be administered (and are attached):

Beck Depression Inventory. Note: the BDI includes a question about suicidal thoughts. If a subject endorses this item research staff will follow the attached suicidality protocol.

MacNew Cardiac Health Status Questionnaire

TCAP

Interpersonal Support Evaluation List

International Physical Activity Questionnaire (IPAQ, brief form)

Executive Function Battery Questionnaires:

The Time Perspective Questionnaire – Exercise (TPQ)

Euroqol (Quality of Life)

Achenbach System of Empirically Based Assessments (ASEBA) – Adult Self Report or Older Adult Self Report

Behavior Rating Inventory of Executive Function (BRIEF)

Data Collection: Questionnaire Administration Amidst Contact Restrictions (e.g. COVID-19)

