Data Analysis: Treatment conditions will be compared for differences in baseline demographic characteristics using one-way Analysis of Variance (ANOVA) (or a nonparametric alternative, such as the Kruskal-Wallis Test) for continuous measures and chi-square tests (or Fisher's Exact Test) for categorical variables. If specific characteristics differ significantly across treatment conditions and are predictive of treatment outcomes, they will be considered as covariates in subsequent analyses. Primary analyses will include all subjects randomized to treatment conditions independent of early dropout or non-adherence, consistent with an intent-to-treat approach for randomized clinical trials.¹⁴⁷

The primary outcome measure in this trial will be CR adherence (% completing 30+ sessions) compared between the control condition and any of the three intervention conditions as well as between the combined intervention and either of the interventions delivered alone. Proportions completing all CR sessions will be examined across conditions using the test for differences between two population proportions (z), with 95% confidence intervals on effect sizes. To look at other measures of attendance, Cox proportional hazard models will be used to test differences in number of CR sessions completed

(i.e., time to dropout) between conditions. Purposeful selection of covariates will be used to build models.¹⁶⁴ Once final models have been derived, we will generate estimated hazard ratios with 95% confidence intervals and graphs of covariate-adjusted survival functions. Across all tests, statistical significance will be defined as $p < 0.05$ (2-tailed).

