Withdrawal Procedures: *Define the precise criteria for withdrawing subjects from the study. Include a description of study requirements for when a subject withdraws him or herself from the study (if applicable).*

There are no predefined criteria for withdrawal from the study. However, participants may be withdrawn if the medical director ([name]) determines it is not advisable that they continue on in the program. Participants may withdraw themselves at any time, for any reason. Research data gathered from such participants will be not be retained.

Sources of Materials: Identify sources of research material obtained from individually identifiable human subjects in the form of specimens, records or data. Indicate whether the material or data will be obtained specifically for research purposes or whether use will be made of existing specimens, records or data.

Data for this project will come from clinical records (number of cardiac rehabilitation sessions completed, cause and cost of hospitalizations) or from research procedures: demographics, physical exams, CO measurements, exercise tolerance testing, administered questionnaires, executive function/decision making measures.

To track CR attendance and monitor adverse events among NMC patients, UVMMC research staff will obtain a secure research login to access the electronic medical record at NMC.

DRUG AND DEVICE INFORMATION

Investigators are encouraged to consult the UVM Medical Center Investigational Pharmacy Drug Service ([name]) prior to finalizing study drug/substance procedures.

Drug (s)

Not applicable

Drug name – generic followed by brand name and common abbreviations. Availability – Source and pharmacology; vial or product sizes and supplier. If a placebo will be used, identify its contents and source. (attach investigational drug brochure)

Preparation: Reconstitution instructions; preparation of a sterile product, compounded dosage form; mixing guidelines, including fluid and volume required. Identify who will prepare.

Storage and stability – for both intact and mixed products.

Administration – Describe acceptable routes and methods of administration and any associated risks of administration.

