By definition, primary outcome data will not be missing since it focuses on program participation. For other variables, minor amounts of missing data, due to factors other than dropout from the CR program, will be ignored, leading to deletion of cases in regression analyses. However, if substantial amounts of missing data of key predictor variables exist, we will explore the randomness of missing data using Little's MCAR (missing completely at random) test in SPSS 24. If we cannot reject the null hypothesis, we will proceed to use multiple imputation procedures in SAS 9.4 (PROC MI and PROC MIANALYZE) to generate results based on imputed data.

Although this study is powered for our primary outcome of adherence to CR, we will also carefully examine improvements in fitness, and other health outcomes (quality of life, maximal exercise capacity, weight, waist measurements) between conditions, using the pre-planned comparisons outlined for the primary outcome. Additionally, we will examine changes in executive function measures and socio-cognitive status at 4 and 12 months. Changes in these scores will also be examined for possible gender interactions. Since multiple observations for each participant will be obtained, the general analytic approach will consist of analysis of covariance (ANCOVA) at 4 months and repeated measures analysis of variance (ANOVA) at 12 months. Formal testing will examine the condition by time interaction term to assess differential time changes between treatment conditions. Post-hoc comparisons between conditions will be made if significant interactions are observed.

Survival analyses will be conducted once all participants have completed the 36 sessions of their CR program (or, alternatively, have dropped out of the program). Preliminary analyses of all other outcome measures will occur upon collection of all 4-month measures across all participants. Final analyses of secondary outcome measures, using repeated measures procedures, will be conducted upon collection of all 12- month measures across all participants. Across all tests, statistical significance will be defined as $p < 0.05$ (2-tailed).

Cost Effectiveness Analyses

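### The withdrawal rule discards research data with no stated exception, which as written conflicts with analysing everyone randomised and with a primary outcome that cannot be missing

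*Combined protocol and SAP*

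**What the plan says.** The protocol's Withdrawal Procedures let participants leave at any time. They also allow withdrawal when the medical director "determines it is not advisable that they continue on in the program". The section ends: "Research data gathered from such participants will be not be retained". It lists no exception.

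The next section, Sources of Materials, begins: "Data for this project will come from clinical records (number of cardiac rehabilitation sessions completed, cause and cost of hospitalizations". It then names a second source, research procedures, which covers demographics, exercise testing, questionnaires and executive function measures.

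The protocol (Data Analysis) and the SAP (Primary and Secondary Data Analyses) both commit to intent-to-treat: "Primary analyses will include all subjects randomized to treatment conditions independent of early dropout or non-adherence". On missing data the SAP says: "By definition, primary outcome data will not be missing since it focuses on program participation". For other variables, minor missingness that does not come from CR dropout "will be ignored, leading to deletion of cases in regression analyses". If key predictors have substantial missingness, the SAP applies Little's test and, if that does not reject, multiple imputation.

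Two other places bear on what counts as research data. Allocation is held in the "Interactive Voice Recognition (IVR) system maintained by the Medical Biostatistics Unit at the University of Vermont" (SAP, Randomization). If clinics stop in-person visits, sessions are counted remotely, and "one session will consist of completing a recommended step goal for that day, as confirmed by an Omron pedometer" (protocol, section on CR sessions amid contact restrictions).

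**The concern.** If a withdrawn participant's session count is discarded, that person cannot be analysed as randomised and the primary outcome is missing. Because the SAP treats this as impossible, it does not say whether such a person counts as a non-completer, is imputed, or leaves the denominator.

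Leaving the denominator is the harmful case. An arm's completion rate is inflated when its withdrawers complete below that arm's own rate. The between-arm difference can then move either way, depending on how many withdraw from each arm. Deletion may also be irreversible, so the rule is best settled before any data are destroyed.

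There is a smaller, secondary issue. Baseline exercise capacity, executive function, socio-cognitive status and quality of life are candidate covariates for the Cox models of sessions completed. They come from research procedures, so they would be lost on either reading of the rule. This matters only if those variables are selected into the model.

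**Working it through.** **1. The text.** Three statements are involved: withdrawn participants' research data are not kept; all randomised subjects are analysed; the primary outcome is never missing. With one or more withdrawals, all three hold only if session counts and allocation fall outside research data. No section says that they do.

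**2. Planning inputs.** The protocol's Power section gives 28% completion in usual care and 54% with incentives, tested two-sided at 0.05, with 38 and 57 participants. A likelihood-ratio power calculation at these rates gives 0.804 with 56 per arm and 0.811 with 57, which agrees with the SAP's 56 and the protocol's 57. The total is 3 × 57 + 38 = 209, with no visible allowance for withdrawal. The planned difference is 54 − 28 = 26 points. All withdrawal rates below are assumptions.

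**3. Effect of deletion on the difference.** Let *p* be the arm's true completion rate, *w* the fraction withdrawn and *c* the completion rate among withdrawers. The rate among those kept is (p − w·c)/(1 − w).

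With c = 0:
- Usual care: 0.28/0.95 = 29.5%; 0.28/0.90 = 31.1%; 0.28/0.80 = 35.0%.
- Incentives: 0.54/0.95 = 56.8%; 0.54/0.90 = 60.0%; 0.54/0.80 = 67.5%.

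| Withdrawn (usual care / incentives) | Difference, c = 0 | Difference, c = p/2 | Difference, c = p |
|---|---|---|---|
| 5% / 5% | 27.4 | 26.7 | 26.0 |
| 10% / 10% | 28.9 | 27.4 | 26.0 |
| 10% / 5% | 25.7 | 25.9 | 26.0 |
| 5% / 10% | 30.5 | 28.3 | 26.0 |
| 20% / 5% | 21.8 | 23.9 | 26.0 |
| 5% / 20% | 38.0 | 32.0 | 26.0 |

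The comparison that matters is *c* against *p*. It is not enough that most withdrawers fail to complete. With 10% withdrawn from usual care and 40% of them completing, most are non-completers, yet the kept rate falls to (0.28 − 0.10 × 0.40)/0.90 = 26.7%.

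**4. Type I error.** Take 28% true completion in both arms and c = 0. The kept sample sizes are 38(1 − w) and 57(1 − w), rounded. The pooled two-sided z-test at 0.05 is enumerated exactly.

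| Withdrawn (usual care / incentives) | Kept n | Type I error |
|---|---|---|
| none | 38 / 57 | 4.9% |
| 5% / 5% | 36 / 54 | 4.9% |
| 10% / 10% | 34 / 51 | 5.0% |
| 10% / 5% | 34 / 54 | 5.4% |
| 5% / 10% | 36 / 51 | 5.4% |
| 8% / 2% | 35 / 56 | 5.5% |
| 20% / 5% | 30 / 54 | 8.5% |
| 5% / 20% | 36 / 46 | 8.0% |
| 30% / 15% | 27 / 48 | 9.5% |

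Inflation depends on the amounts withdrawn as well as their ratio: twofold imbalance at 30%/15% does more harm than fourfold at 8%/2%.

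**5. What a sensitivity range would look like.** Suppose 2 of 38 and 3 of 57 are deleted, leaving 11 and 31 completers among those kept.
- Deletion: 31/54 − 11/36 = 26.9 points.
- All counted as non-completers: 31/57 − 11/38 = 25.4.
- All counted as completers: 34/57 − 13/38 = 25.4.
- Opposite extremes: 31/57 − 13/38 = 20.2 and 34/57 − 11/38 = 30.7.

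**The case against.** The strongest reply is that the rule was never meant to reach attendance. Sources of Materials separates clinical records, including session counts, from research procedures, and research data most naturally means the second class. Allocation sits in a separate system. On that reading the intent-to-treat commitment and the missing-data statement are both consistent with the rule. This is plausible and would remove most of the primary-outcome conflict. It remains an inference, because the same section lists session counts among the project's data and no sentence exempts them. Remote sessions confirmed by pedometer would still be in doubt, and baseline research measures would still go.

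Several limits stand in full:
- A reader might infer that everyone who stops CR is lost. The documents do not support this. Someone who stops attending but stays in the study remains in the analysis as a non-completer.
- A reader might infer that the SAP removes withdrawers from the Cox models by case deletion. That rule covers only minor missingness not caused by CR dropout, and imputation is provided for substantial missingness. Those models are also secondary; the primary test is an unadjusted comparison of two proportions.
- Withdrawers need not be failures. Under Therapeutic Alternatives, patients are told that CR is open to them outside the study.
- With 5% to 10% withdrawal per arm, type I error is 4.9% to 5.4% even if no withdrawer completes.

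**Conclusion.** The rule is wrong as written and should be fixed. It contradicts the analysis population and the missing-data statement, and it leaves the SAP without a method for withdrawn participants. The contradiction is textual and does not depend on any assumed rate.

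Its practical size is unknown, because no withdrawal rate is given. It is nil if nobody withdraws, if session counts are in fact kept, or, in expectation, if withdrawers complete at their arm's rate. If session counts are deleted and no withdrawer completes, the 26-point difference shifts by 1.4 to 2.9 points at equal withdrawal of 5% to 10%. Larger unequal withdrawal moves it to between 21.8 and 38.0 points in the cases shown, with type I error of 8.0% to 9.5%.

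A reader might go further and conclude that the primary result will be biased, or biased in favour of the interventions. The documents do not support that. They fix neither the direction nor the amount, and they do not establish that attendance will in fact be deleted. Confidence is medium because the narrower reading may be the intended one.

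**What to change.** Replace the sentence in Withdrawal Procedures so that allocation, baseline data and session counts collected up to withdrawal are retained. Keep every randomised participant in the assigned arm in the primary analysis. After withdrawal, use clinical attendance records where the participant permits it. Otherwise, count a session total below the primary threshold as non-completion.

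If attendance records were never meant to be covered, say so there. State whether remote sessions are treated the same way, and whether the rule also applies to withdrawals by the medical director. Report withdrawals by arm and by who initiated them.

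Honour any promise of deletion already made. For every withdrawer whose final attendance is not observed, whether through deletion or lack of permission, report the primary contrast with all counted as non-completers, all as completers, and the opposite extremes by arm. This group must include people coded as non-completers by default, since they may have finished CR elsewhere and permission may differ by arm. Amend the SAP's statement that the primary outcome cannot be missing to match.

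The cost is a short amendment with IRB approval, plus a consent change if the consent form (not among the documents reviewed) promises deletion. Data up to withdrawal are already collected. Using attendance records after withdrawal is continued collection and needs permission. The sensitivity range needs only the number of such participants per arm.
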